9.6 Exploratory Analysis

Analyses related to the exploratory endpoints of changes in inflammatory mediators and changes in microbiology analysis from baseline will be discussed in a separate document.

9.6.1 Analysis of absolute change from baseline in CFQ-R non-respiratory domain score

Analysis of these domains will be based on an MMRM similar to the analysis of the absolute change from baseline in ppFEV₁. The mean plot will not be produced for these domains.

10 Interim and DMC Analyses

10.1 Interim Analysis

As mentioned in the protocol, IA for study 110 may take place at any time during the study at the discretion of the sponsor.

10.2 DMC Analysis

An independent data monitoring committee (IDMC) was formed before initiation of study 110. The IDMC's objectives and operational details are described in the IDMC charter. The IDMC will conduct regular planned safety reviews of study data as outlined in the IDMC Charter and IDMC Analysis Plan.

12 APPENDICES

12.1 Analysis Visit Windows for Safety and Efficacy Assessments

Table 12-1 Analysis Visit Windows for Safety and Efficacy Assessments			
Assessment	Visit¹	Target Study Day	Analysis Visit Window (in study days)^{2, 3,4,5}
Spirometry Weight, Height and BMI (and the corresponding z-score) ⁶	Parent study baseline	--	≤1 corresponding to the first dose date of parent study
	OL Day 15	15	(1, 22]
	OL Week 4	29	(22, 43]
	OL Week 8	57	(43, 85]
	OL Week 16	113	(85, 141]
	OL Week 24	169	(141, 211]
	OL Week 36	253	(211, 295]
	OL Week 48	337	(295, 379]
	OL Week 60	421	(379, 463]
	OL Week 72	505	(463, 547]
	OL Week 84	589	(547, 631]
OL Week 96	673	(631, 687]	
	OL Safety Follow-up	Not applicable	>687
Sweat Chloride	Parent study baseline	--	≤1 corresponding to the first dose date of parent study
	OL Day 15	15	(1, 22]
	OL Week 4	29	(22, 43]
	OL Week 8	57	(43, 113]
	OL Week 24	169	(113, 253]
	OL Week 48	337	(253, 421]
	OL Week 72	505	(421, 589]
	OL Week 96	673	(589, 687]
CFQ-R	Parent study baseline	--	≤1 corresponding to the first dose date of parent study
	OL Week 4	29	(1, 43]
	OL Week 8	57	(43, 113]
	OL Week 24	169	(113, 253]
	OL Week 48	337	(253, 421]
	OL Week 72	505	(421, 589]
	OL Week 96	673	(589, 687]
		OL Safety Follow-up	Not applicable

Table 12-1 Analysis Visit Windows for Safety and Efficacy Assessments			
Assessment	Visit¹	Target Study Day	Analysis Visit Window (in study days)^{2, 3,4,5}
Hematology Serum Chemistry Vital Signs	TC safety baseline	1	defined in section 8.1
	OL Day 15	15	[1, 22] where day 1 is
	OL Week 4	29	postdose measurement
	OL Week 8	57	(22, 43]
	OL Week 16	113	(43, 85]
	OL Week 24	169	(85, 141]
	OL Week 36	253	(141, 211]
	OL Week 48	337	(211, 295]
	OL Week 60	421	(295, 379]
	OL Week 72	505	(379, 463]
	OL Week 84	589	(463, 547]
	OL Week 96	673	(547, 631]
	OL Safety Follow-up	Not applicable	(631, 687] Use nominal visit
Standard 12-lead ECG	TC safety baseline	1	defined in section 8.1
	OL Day 15	15	[1, 22] where day 1 is
	OL Week 4	29	postdose measurement
	OL Week 8	57	(22, 43]
	OL Week 24	169	(43, 113]
	OL Week 48	337	(113, 253]
	OL Week 72	505	(253, 421]
	OL Week 96	673	(421, 589]
		OL Safety Follow-up	Not applicable
Coagulation	TC safety baseline	1	defined in section 8.1
	OL Week 4	29	[1, 99] where day 1 is
	OL Week 24	169	postdose measurement
	OL Week 48	337	(99, 253]
	OL Week 72	505	(253, 421]
	OL Week 96	673	(421, 589]
		OL Safety Follow-up	Not applicable

Notes:
 
¹ Visit name for analysis purpose is used to report data in tables and figures.
 
² The analysis visit windows will be applied using the following rules for both scheduled and unscheduled visits:
 
 1. If no numerical measurement is available within a visit window, the measurement will be considered missing for the visit. 2. If there is more than 1 numerical measurement available within a visit window, use the following rules: 
 i. The measurement closest to the target day will be used; or ii. If there are multiple measurements with the same closest distance from the target day, the latest measurement will be used. For multiple measurements on the same day, unscheduled measurements will be treated as later than scheduled measurement. 
³ For measurement collected on the date of first dose of study drug in Treatment Period, if it cannot be determined whether the measurement is before or after the first dose:
 
 a. Scheduled measurement will be treated as pre-dose observation. b. Unscheduled measurement will be treated as post-dose observation. 			

Table 12-1 Analysis Visit Windows for Safety and Efficacy Assessments			
Assessment	Visit¹	Target Study Day	Analysis Visit Window (in study days)^{2, 3,4,5}

⁴ For safety Assessment, Safety Follow-up analysis visit will be based on nominal Safety Follow-up visit. If a subject doesn't have a nominal Safety Follow-up visit but has an ETT visit with study day >687, then the ETT visit will be mapped into Safety Follow-up analysis visit.
 
⁵ For efficacy assessment, if a subject has nominal safety follow up visit with study day >687, then nominal Safety Follow-up visit will be mapped to Safety Follow-up visit; else if subject doesn't have a nominal safety follow-up visit with study day > 687 but has an ETT visit with study day >687, then the ETT visit will be mapped into Safety Follow-up analysis visit; else if there are multiple assessments with >687 then select the earliest record.
 
⁶Weight will also be used in the threshold analysis in which the TC safety baseline will be used to calculate change.
 
Derived Variables:
 
 Age (in years) at first dose date and post-baseline visit (for demographics, listing and the calculation of [percent] predicted spirometry variables): 
Obtain the age at informed consent in “yy, mm” format (e.g., 24 years, 6 months) in parent study from the Vital Signs (VS) page at the Screening Visit in parent study, and add 0.5 month to convert to days.
 
Obtain the informed consent date in parent study.
 
Then age (in years) at first dose or post-baseline visit = [(first dose date or post-baseline visit date – informed consent date in parent study) in days + age at informed consent (in days) in parent study]/365.25.
 Age (in months) at first dose date and post-baseline visit (for use in calculation of BMI and weight z-score): 
Obtain the age at informed consent in “yy, mm” format (e.g., 24 years, 6 months) in parent study from the VS page at the Screening Visit in the parent study.
 
Obtain the informed consent date in parent study.
 
Then age (in months) at first dose or post-baseline visit = integer part of {[age at informed consent (in months) in parent study + 0.5 + diff(first dose date or post-baseline visit date, informed consent date) in months in parent study]} + 0.5.
 Missing first dose date or last dose date 
If the first dose date is missing, use Day 1 visit date.
 
If the last dose date of study drug is not available and there is no data to indicate that the subject discontinued treatment, the data cutoff date will be used instead.
 
If the subject discontinued treatment and the last dose date is missing or partial date is reported, the last dose date will be imputed based on, in descending order priority, the Early Treatment Termination (ETT) visit date, last visit date before the Safety Follow-up, or the last study drug administration date from EX SDTM domain, as appropriate. The imputation algorithm will ensure the imputed last dose date does not exceed the study participation end date.
 Electrocardiogram: 
Baseline is defined in Section 8.1. If multiple ECG measurements are obtained on the same calendar day during the TE period for Part A,
 
 ○ For summary purpose, the average value will be used as the ECG on that day; ○ For threshold analysis purpose, all ECG values will be used 			

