12.3.3.2 Analysis of Secondary Efficacy Endpoints

The secondary endpoints include:

- **Absolute change in ppFEV₁**

One of the secondary efficacy endpoints is the absolute change in ppFEV₁ at visits in the open-label study, for subjects who receive at least 1 dose of study drug in the open-label study. The primary analysis for this secondary endpoint will be based on a mixed-effects model for repeated measures (MMRM), with the absolute change from baseline in ppFEV₁ as the dependent variable for visits in the open-label study. The model will be similar to the one used for the primary efficacy analysis in the parent study.

The details including sensitivity analyses and supportive analyses will be described in the SAP.

- **Absolute change in SwCl**

Analysis of this PD endpoint will be based on an MMRM similar to the analysis of the absolute change in ppFEV₁.

- **Absolute change in BMI**

Analysis of this endpoint will be based on an MMRM similar to the analysis of the absolute change in ppFEV₁.

- **Absolute change in BMI z-score**

Analysis of this endpoint will be based on an MMRM similar to the analysis of the absolute change in ppFEV₁.

- **Absolute change in body weight**

Analysis for this endpoint will be based on an MMRM similar to the analysis of the absolute change in ppFEV₁.

- **Absolute change in CFQ-R RD score**

Analysis of this endpoint will be based on an MMRM similar to the analysis of the absolute change in ppFEV₁.

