Vertex recommends that subjects and sites refer to local guidance regarding travel restrictions. There are no operational changes to the study protocols for subjects who can travel to the study sites for their visits. However, to ensure continued safety of subjects who *cannot* travel to the study sites for their visits (for any reason due to COVID-19), specific alternative measures are being implemented to minimize the risk of exposure to COVID-19 (see table below). As the COVID-19 pandemic evolves, Vertex will continue to assess the need for additional actions to ensure the safety of all involved in these clinical studies.

Addendum Version 3.0 summarizes additional measures taken for these ongoing CF clinical studies (see table below) to ensure continued safety.

Summary of Changes in Ongoing CF Clinical Studies for Subjects Who Cannot Travel to the Study Site

| Protocol Change | Rationale for Change | Study Number |
|--|--|---|
| Addendum Version 3.0, dated 29 July 2020 | | |
| 
Assessments
 
Unscheduled visit(s) will be permissible at the discretion of the investigator(s) or Vertex. The unscheduled visit(s) may be conducted at any time during the study (including after the protocol defined last study visit) in the event assessments specified to be collected at a scheduled visit were not collected due to COVID-19.
 | 
To ensure subject safety and/or to facilitate evaluation of safety and/or efficacy if assessments are not performed per the schedule in the protocol due to COVID-19.
 | 
[REDACTED]
 
[REDACTED]
 
[REDACTED]
 
[REDACTED]
 
VX18-445-110
 
[REDACTED]
 |
| 
Implementaion of measures described in addenda versions 1.0 and 2.0, as applicable.
 | 
To ensure subject safety and/or to facilitate evaluation of safety and/or efficacy while maintaining study integrity and the safety of subjects and site personnel.
 | 
[REDACTED]
 |

Summary of Changes in Ongoing CF Clinical Studies for Subjects Who Cannot Travel to the Study Site

| Protocol Change | Rationale for Change | Study Number |
|---|--|---|
| Addendum Version 2.0, dated 15 May 2020 | | |

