8.2 Open Label Extension Period

OL Efficacy Period for Part A: The time from the first dose of study drug in the OLS to the last efficacy assessment, which may be collected up to the Week 96 Visit or the earlier of Day 673 and the end of study participation if subject does not have the Week 96 Visit. This analysis period will be used with the OL-FAS for Part A to analyze the efficacy data during the OLS.

OL Safety Period for Part A: The time from the first dose of study drug in the OLS to 28 days after the last dose date of the study drug in the OLS or to the completion date of study participation (defined in CSP Section 9.1.5) in Part A, whichever occurs first. This analysis period will be used with the OL-SS for Part A to analyze the safety data during the OLS.

The **Treatment-emergent (TE) Period for Part A** is same as the OL Safety Period for Part A.

Note: for subjects who depart study 110 to participate in another qualified Vertex study and return in study 110, the above defined analysis period will exclude the time between the last dose before the discontinuation from study 110 and the first dose after re-enter in study 110.

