9 STATISTICAL ANALYSIS

9.1 General Considerations

The precision standards for reporting safety and efficacy variables are provided in an internal Biometrics document that specifies the programming rules including the precision for derived variables.

Data will be summarized by treatment group in the parent study (“Control in 445-104” and “ELX/TEZ/IVA in 445-104”) and overall (“Any ELX/TEZ/IVA”).

Continuous variables will be summarized using the following descriptive summary statistics: the number of subjects (n), mean, standard deviation (SD), median, minimum value (min), and maximum value (max).

Categorical variables will be summarized using counts and percentages. Percentages will be presented to 1 decimal place.

Baseline value for clinical laboratory values, standard 12-lead ECGs, vital signs, and pulse oximetry will be the TC safety baseline defined as the most recent non-missing measurement (scheduled or unscheduled) collected before the first dose of study drug in the parent study (if the subject actually received at least one dose of ELX/TEZ/IVA during the parent study) or the first dose of study drug in the OLS (if the subject did not actually receive at least one dose of ELX/TEZ/IVA during the parent study). **Baseline value** for efficacy analyses, demographics, and baseline characteristics will be the parent study baseline defined as the most recent non missing measurement (scheduled or unscheduled) collected before the first dose of study drug in the Treatment Period of the parent study.

Change (absolute change) from baseline will be calculated as post-baseline value – baseline value. **Relative change** from baseline will be calculated as (post-baseline value – baseline value)/baseline value.

Unscheduled visits: Unscheduled visit measurements will be included in analysis as follows:

- 1) In scheduled visit windows per specified visit windowing rules
- 2) In the derivation of baseline
- 3) In the derivation of maximum and minimum values during TE period for Part A, and maximum and minimum change from baseline values during TE period for Part A for the long-term safety analyses
- 4) In individual subject data listings as appropriate

Visit windowing rules: The analysis visit windows for protocol-defined visits are provided in Section 12.1.

Incomplete/missing data will not be imputed, unless specified otherwise.

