9.3.2.1 Analysis Method

Absolute change from baseline in ppFEV₁

The MMRM for the parent study efficacy period will be same as that described in the SAP for Study 104. In the MMRM for the OL efficacy period for Part A, the absolute change from baseline in ppFEV₁ will be the dependent variable. The model will include treatment group (as randomized in parent study), visit, and treatment by visit interaction as fixed effects, with continuous baseline ppFEV₁ from parent study, continuous baseline SwCl from parent study and comparator group (IVA comparator versus TEZ/IVA comparator) as covariates.

The repeated-measures analysis will be based on the restricted maximum likelihood method assuming an unstructured covariance structure to model the within-subject errors. The denominator degrees of freedom will be based on the method proposed by Kenward-Roger⁶. If the model fails to converge due to the unstructured covariance assumption, a compound symmetry covariance structure will be used to model the within-subject errors. In the MMRM approach, assuming that the data are missing at random, no imputation of missing data will be performed.

The number of subjects, least-squares means (LS means) for absolute change from baseline at scheduled visits within each treatment group along with the corresponding standard error (SE), and 95% confidence interval (CI) will be presented. The LS means (\pm SE) for absolute change from baseline at each visit will also be plotted by treatment groups. For display purpose, the estimates and corresponding 95% CI obtained from both the parent study MMRM and OLS Part A will be summarized in a single summary table.

The main analysis will be conducted with the clinic spirometry data only. In addition, the descriptive statistics for raw values and absolute changes from baseline in ppFEV₁ by treatment group and visit will be presented for the OL efficacy period for Part A in OL-FAS for Part A.

Absolute change from baseline in SwCl

Analysis of this PD variable will be based on the same MMRM to the analysis of the absolute change from baseline in ppFEV₁. A descriptive summary of raw values and absolute changes from baseline will also be presented.

Absolute change from baseline in Weight, BMI and BMI Z-score (for subjects \leq 20 years of age at parent study baseline)

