9.3.2.1 Sensitivity and Supportive Analysis of Secondary Endpoints

No sensitivity or supportive analysis is planned for the secondary endpoints.

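### Do the Day 673 limit in SAP 8.2 and the Day 687 window in Table 12-1 leave the Week 96 efficacy data undefined?

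*SAP*

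**What the plan says.** SAP 8.2 runs the OL Efficacy Period for Part A from the first open-label dose to the last efficacy assessment. That assessment may be taken up to the Week 96 Visit or, failing that, up to "the earlier of Day 673 and the end of study participation if subject does not have the Week 96 Visit". The same section says this period, with the OL-FAS, is what the efficacy analysis uses.

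Table 12-1 in SAP 12.1 gives Week 96 (target Day 673) the window (631, 687] for spirometry, weight and BMI, and (589, 687] for sweat chloride and CFQ-R. SAP 9.1 places unscheduled values "In scheduled visit windows per specified visit windowing rules", and note 2 to the table agrees: "The analysis visit windows will be applied using the following rules for both scheduled and unscheduled visits". Note 5 covers efficacy values at follow-up: "if a subject has nominal safety follow up visit with study day >687, then nominal Safety Follow-up visit will be mapped" to the Safety Follow-up row. Note 4 uses the nominal follow-up visit for safety data.

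For ppFEV₁, SAP 9.3.2.1 (Analysis Method) states: "The main analysis will be conducted with the clinic spirometry data only". Protocol 12.3.3.2 says of that endpoint: "The details including sensitivity analyses and supportive analyses will be described in the SAP". The SAP's answer is: "No sensitivity or supportive analysis is planned for the secondary endpoints".

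**The concern.** For a subject without a Week 96 Visit, a value on Days 674 to 687 is a Week 96 value by the table and lies outside the efficacy period by Section 8.2. No sentence ranks the two. Week 96 is the last efficacy time point of Part A, so different readings could give different final data sets.

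COVID-19 Addendum 3.0 seems to widen the gap, because missed assessments may be made up at an unscheduled visit even after the last protocol visit. Clinic spirometry made up on Day 680 could be in or out, possibly for a subject still on drug.

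A second worry is that a subject who stops early has a Safety Follow-up visit 21 to 35 days after the last dose, and that value can fill a treatment-visit row. The SAP does not comment on this and plans no supportive analysis, so a reader might doubt whether the long-term means are meant to include off-drug data.

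**Working it through.** **Reproducing the plan's days.** Week 96 target: 7 × 96 + 1 = 673. The visit window of ±5 days (Protocol Table 3-1) gives Days 668 to 678. Dosing ends the evening before the visit, so the last dose falls on Days 667 to 677. Follow-up 21 to 35 days later falls between 667 + 21 = 688 and 677 + 35 = 712. A window closing on Day 687 therefore admits every on-time Week 96 Visit and excludes every on-time completer's follow-up.

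**Who meets the conflict.** Day 673 applies only without a Week 96 Visit. The disputed days number 687 − 673 = 14. Follow-up lands on them if the last dose was on Days 653 to 666 (21-day gap), 646 to 659 (28-day) or 639 to 652 (35-day).

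**Worked example.** Last dose Day 652, ETT Day 655, follow-up Day 680. Distances from target are 673 − 655 = 18 and 680 − 673 = 7. The table alone selects Day 680. Applying the period first removes Day 680 and selects Day 655.

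**Counting.** Take each last-dose day from 2 to 667 (666 days), ETT at +1, +3, +7 or +14 days, follow-up at +21, +28 or +35, and the rule of closest to target, then latest. Compare the Week 96 selection under a limit of 673 and of 687.

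- Spirometry and CFQ-R both differ on 8 to 18 days: 8/666 = 1.2%, 18/666 = 2.7%.
- On 0 to 8 of those days the 673 limit leaves Week 96 empty.
- Subjects affected = 250 × stopping rate × share. At 5%: 0.15 to 0.34. At 10%: 0.30 to 0.68. At 20%: 0.60 to 1.35.

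**Off-drug values up to Day 673.** Over all 666 days, the follow-up value is selected for some treatment visit on 54 to 70% of last-dose days for spirometry and 52 to 60% for CFQ-R. With ETT at +7 and follow-up at +28 the shares are 62.5% and 55.9%. At 10% stopping this gives 250 × 0.10 × 0.625 ≈ 16 spirometry values over 11 visits and 250 × 0.10 × 0.559 ≈ 14 CFQ-R values over 6 visits. These are upper counts, because they give every stopper a separate follow-up visit. Protocol 9.1.2 and 9.9 remove that visit for subjects who move to commercial or managed-access treatment or to another qualified study.

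**Effect on the means.** Assume 125 per arm.

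- ppFEV₁, SD 7: SE = 7/√125 = 0.63. With correlation 0.7, 10% stopping and 5 points lost off drug, simulation of the repeated-measures model gives a Week 96 shift of 0.08 (0.08/0.63 = 13% of the SE). The range is 0.02 (5%, 3 points) to 0.35 (20%, 10 points).
- A closed-form check of the ppFEV₁ case gives 0.077 with limit 673 and 0.084 with limit 687. The choice of limit itself is thus worth 0.084 − 0.077 = 0.007 points.
- CFQ-R respiratory domain, SD 16: SE = 16/√125 = 1.43. With correlation 0.6, 10% stopping and 10 points lost, the shift is 0.24 (17% of the SE), range 0.06 to 1.07.

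**Make-up visits.** If a fraction f of Week 96 values were dropped, the SE rises by √(1 + (1 − R²) f/(1 − f)) − 1, with R² = 10ρ²/(1 + 9ρ). At ρ = 0.7, R² = 4.9/7.3 = 0.67. For f = 5, 10 and 20% the rise is 0.9, 1.8 and 4.0% (0.4 to 6.6% over ρ from 0.5 to 0.85). The documents give no basis for any value of f.

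**The case for a change.** The case for a change is that both rules are operative and unranked. The table even carries an efficacy row after Day 687, which lies outside the 8.2 period for anyone with an on-time Week 96 Visit or with none, so it was not built as a subset of that period. One sentence would settle it at almost no cost.

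The textual mismatch stands. But that late row cuts the other way too: having a row in the table does not put a value in the model. SAP 8.2 names the data the efficacy analysis uses, and SAP 9.3 and 9.3.2.1 tie the open-label model to that period. To reach a different Week 96 data set, a programmer would have to set 8.2 aside.

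The make-up argument keeps a small residue. Visits could be held at home, and the Part B transition note under SAP Figure 6-1 presupposes a Part A Week 96 Visit, so the Day 673 limit should rarely apply to subjects still on drug. Whether clinic spirometry made up later belongs to a Week 96 Visit held at home is not spelled out. The two-part protocol that the SAP follows was not available to check this. Leaving such values out costs some precision.

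On off-drug values, the rules already decide. The efficacy period can run to the end of participation, which Protocol 9.1.5 sets at the Safety Follow-up Visit or the visit replacing it. In the same SAP section the safety period is cut relative to the last dose and the efficacy period is not. Protocol 12.3.1 does not cut efficacy at last dose either. This is a coherent treatment-policy reading, and stating the intent would add explanation without altering a rule. On supportive analyses, the protocol left the matter to the SAP, and the SAP says there are none.

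**Conclusion.** No change follows. The 673/687 mismatch is real but confined to subjects without a Week 96 Visit and, perhaps, a few make-up assessments. It is a gap that analysts fill sensibly by applying the 8.2 period and then the windows. It touches about 0.15 to 1.35 of 250 subjects at an assumed 5 to 20% stopping rate with last-dose days spread evenly, and moves the Week 96 ppFEV₁ mean by about 0.007 points in the 10% case.

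Counting off-drug values has a larger effect, about 0.08 points of ppFEV₁ against an SE of 0.63. In the most adverse assumed corners it reaches 0.35/0.63 = 56% of the SE for ppFEV₁ and 1.07/1.43 = 75% for CFQ-R. That is the consequence of a defensible rule the documents already contain, so an on-treatment model would be an optional extra. Sweat chloride is not collected at follow-up. The affected endpoints are secondary or exploratory, no P values are planned, and the primary safety objective is untouched.

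Stopping rate, off-drug loss, SD, correlation and make-up rate are all assumptions. The visit timings come from the single-part protocol.
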